10.1.2.3 Missing and Partial Dates of Medical History Diseases

As no calculations on start and stop dates will be done, no imputation of missing or partially missing dates will be performed. If the medical condition is ongoing at study start, this is indicated via the checkbox in the eCRF.

10.1.3 Reference Start Date and Analysis Day

The treatment date will be the reference start date.

Analysis day will be calculated from the reference start date and will be used to show start/end day of assessments, events, diseases, therapies, or procedures.

In the situation where the assessment/event/disease/therapy/procedure date is fully missing and cannot be imputed (i.e., when an adverse event, a disease, a therapy, or a procedure is reported as being ongoing), analysis day will be missing.

10.1.4 Descriptive Statistics

For the descriptive statistics, unless otherwise noted, the categorical endpoints will be summarized by frequencies and proportions expressed as percentages (n, %) of subjects for each classification category, and the continuous endpoints will be summarized using standard descriptive statistics (n, mean, standard deviation, median, min and max).

10.1.5 Statistical Tests and Confidence Intervals

A one-sided type I error $\alpha = 0.025$ will be used to declare statistical significance for the primary endpoint CCI. Confidence intervals (CIs) will be two-sided with 95% coverage for the primary endpoint CCI.

10.1.6 Decimal Precision

Unless otherwise noted, the following rounding conventions will be applied:

- Means, medians, first and third quartiles will be rounded and presented to one more decimal digit than the source data.
- CIs of means will be rounded and presented to one more decimal digit than the source data.
- Standard deviations will be rounded and presented to two more decimal digits than the source data.
- Minima and maxima will be presented to the same number of decimal digits as the source data.
- Proportions will be reported as percentages (not as fraction of unit).

 EST. 1981	Title 43CH2305 Statistical Analysis Plan	Doc id MA-59378
---	--	---------------------------

Study Number 43CH2305
Statistical Analysis Plan

CONFIDENTIAL

Page 24 of 36
Final, 1.0, date 24APR2024

- Percentages will be rounded and presented to one decimal digit; percentages equal to 0 will be presented as '0'.
- CIs of percentages will be rounded and presented to one decimal digit.
- Standard errors of percentages will be rounded and presented to two decimal digits.
- P-values greater than or equal to 0.0001 and lower than or equal to 0.9999 will be rounded and presented to fourth decimal digits.
- P-values lower than 0.0001 will be presented as '< 0.0001'.
- P-values greater than 0.9999 will be presented as '>0.9999'.

10.1.7 Software Version

All analyses will be performed using SAS® software Version 9.4 or higher.

10.2 Study Subjects

10.2.1 Disposition of Subjects

The disposition of subjects will be presented in total (based on all screened subjects), including frequencies and proportions (n, %) of subjects that were:

- Screened,
- Eligible,
- Randomized,
- Treated,
- Completed treatment,
- Completed study,
- Withdrawn.

These numbers will also be presented by study site. Reasons for withdrawal will be summarized. Listing for subjects' disposition, screen failures, discontinued subjects, treatment completion status and withdrawal will be provided.

10.2.2 Accounting of Subjects

Frequencies and proportions (n, %) of subjects at each study visit will be summarized overall based on the FAS.

Listings for subject scheduled visits and subject unscheduled visits will be provided.

	
Title 43CH2305 Statistical Analysis Plan
	
Doc id MA-59378

--	--	-----------------------------------

Study Number 43CH2305
Statistical Analysis Plan

CONFIDENTIAL

Page 25 of 36
Final, 1.0, date 24APR2024

10.2.3 Protocol Deviations

Major protocol deviations and major protocol deviations leading to the exclusion from the PPS will be summarized using frequencies and proportions (n, %) of subjects in the FAS for each deviation coded term.

A listing of all protocol deviations will be provided.

10.2.4 Data Sets Analyzed

Frequencies and proportions (n, %) of subjects in each analysis set (FAS, PPS, and SAF) will be summarized by study site and in total based on all randomized subjects.

Listings for inclusion/exclusion criteria not met, and analysis set will be provided.

10.2.5 Demographic and Other Baseline Characteristics

Descriptive statistics (n, mean, standard deviation, median, min and max) or frequencies and proportions (n, %) of subjects for each classification category (as applicable) will be presented using the FAS for the following demographic data and baseline characteristics:

- Age (years)
- Sex
 - Male
 - Female
 - Female subjects of childbearing potential
- Height (cm)
- Weight (kg)
- BMI (kg/m²)
- Ethnicity
 - Han Chinese
 - Other.

Listings for demographic data and baseline characteristics will be provided.

10.2.6 Medical History, Prior and Concomitant Therapies and Procedures

Prior and concomitant therapies/medications will be coded using WHO Drug Dictionary (version September 2023, or later). Medical history diseases and prior and concomitant medical/surgical procedures will be coded using MedDRA dictionary (version 26.1 or later).

Summaries will be presented using the FAS for the following:

- Frequencies and proportions (n, %) of subjects who had any medical history events by SOC and PT, as well as number of events
- Frequencies and proportions (n, %) of subjects who had medical history events that were ongoing at study start by SOC and PT, as well as number of events

 EST. 1981	Title 43CH2305 Statistical Analysis Plan	Doc id MA-59378
---	--	---------------------------

Study Number 43CH2305
Statistical Analysis Plan

CONFIDENTIAL

Page 26 of 36
Final, 1.0, date 24APR2024

- Frequencies and proportions (n, %) of subjects who had concomitant medications by ATC level 3 and Active Ingredient(s), as well as number of drugs
- Frequencies and proportions (n, %) of subjects who had prior aesthetic procedures or implants by SOC and PT, as well as number of events.
- Frequencies and proportions (n, %) of subjects who had concomitant procedures/non-pharmacological treatments by SOC and PT.

Concomitant medications and concomitant procedure/non-pharmacological treatments will also be presented by reason to why they were given.

Listings of all medical history diseases, prior and concomitant therapies/medications and aesthetic procedures or implants will be provided.

10.2.7 Measurements of Treatment Compliance

10.2.7.1 *Treatment Administration and Procedural Anesthetics*

Treatment administration endpoints that will be summarized by study product and overall include (but are not limited to): injection volume, injection technique, approximate number of injection sites, depth of injection, and needle size.

The number of subjects (n, %) with any post-treatment care will be summarized by study product and type of post-treatment care:

- None
- Massage
- Ice/cooling
- Other.

Listings of treatment administration and procedural anesthetics will be provided.

10.3 Estimands

No estimands are defined for this study.

10.4 Effectiveness Analysis

Primary inference for effectiveness analysis will be based on the FAS at the end of injection (T0). Subjects will be summarized and analyzed according to the treatment they were randomized to (Restylane Skinboosters Vital Lido in the left hand and Restylane Vital in the right, or vice versa). All effectiveness data (including effectiveness data of incomplete treatments) will be listed.

10.4.1 Effectiveness Data Summary

10.4.1.1 *VAS*

VAS scores will be summarized at each timepoint (T0, T10, T20, and T30) using descriptive statistics (n, mean, standard deviation, median, min and max) by study product based on the FAS.

 EST. 1981	Title 43CH2305 Statistical Analysis Plan	Doc id MA-59378
---	--	---------------------------

Study Number 43CH2305
Statistical Analysis Plan

CONFIDENTIAL

Page 27 of 36
Final, 1.0, date 24APR2024

The within-subject differences (Δ_{T0} , Δ_{T10} , Δ_{T20} , and Δ_{T30}) will be summarized at each post-treatment timepoint using descriptive statistics (n, mean, standard deviation, median, min and max) in the total group based on the FAS.

Frequencies and proportions (n, %) of subjects that have a within-subject difference of less than 0 mm on the VAS will be summarized at each post-treatment timepoint (T0, T10, T20, and T30) in the total group in the FAS.

Summaries will be presented overall.

CCI

10.4.2 Analysis of Primary Endpoint

The primary endpoint in this study is defined as the within-subject difference in VAS score (Restylane Skinboosters Vital Lidocaine - Restylane Vital) at the end of injection. The null hypothesis that the within-subject difference in VAS score is greater than or equal to 0 mm will be tested against the alternative hypothesis that the within-subject difference in VAS score is less than 0 mm using a one-sample t-test. See Section 3.3.1 for a more formal description of the statistical hypotheses to be tested.

If the one-sided p-value of the test is <0.025 the pain at the end of injection will be considered statistically significantly lower after treatment with Restylane Skinboosters Vital Lidocaine than after treatment with Restylane Vital, and thus the primary objective will be considered met. Results will include mean VAS score by treatment, mean within-subject difference in VAS, and the p-value along with standard descriptive statistics and the two-sided 95% CI around the difference (based on the t distribution).

The results for the primary endpoint will also be presented by study site, descriptively only.

See Section 10.4.6.3 for handling of missing values.

10.4.3 Sensitivity Analysis of Primary Endpoints

To investigate the assumptions underlying the model, analysis of the distribution of the within-subject differences will be done. If the distribution of the differences seems to be deviating from normal, a Wilcoxon signed-rank test will be used as a sensitivity analysis. However, the statistical hypotheses to be tested will change from the one specified in Section 3.3.1 to the following:

 EST. 1981	Title 43CH2305 Statistical Analysis Plan	Doc id MA-59378
---	--	---------------------------

Study Number 43CH2305
Statistical Analysis Plan

CONFIDENTIAL

Page 28 of 36
Final, 1.0, date 24APR2024

$$\begin{cases} H_0: \tilde{\Delta} \geq 0 \text{ mm} \\ H_1: \tilde{\Delta} < 0 \text{ mm,} \end{cases}$$

[figure not shown]
where $\tilde{\Delta}$ denotes the median within-subject difference in VAS score (Restylane Skinboosters Vital Lidocaine - Restylane Vital) at the end of injection.

To assess the robustness of the primary effectiveness results, the following sensitivity analyses will be conducted:

1. Observed Case (OC) analysis of the within-subject difference in VAS score at T0 on the FAS under Missing Completely at Random assumption,
2. Analysis of the within-subject difference in VAS score at T0 will be repeated on the PPS.

The analyses in 1) and 2) will follow the outline in Section 10.4.2, however, no analyses by study site will be done. If the normality assumption is found to be questionable, 1) and 2) will also be performed using the Wilcoxon signed-rank test.

CCI

	Title 43CH2305 Statistical Analysis Plan	Doc id MA-59378
--	--	---------------------------

Study Number 43CH2305
Statistical Analysis Plan

CONFIDENTIAL

Page 29 of 36
Final, 1.0, date 24APR2024

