7 SAMPLE SIZE CONSIDERATION

Several studies have been performed comparing the same HA-filler product with and without the addition of lidocaine or other analgesics. In the study 43CH1504¹, comparing Restylane for treatment of nasolabial folds with and without Lidocaine in subjects with Chinese ethnicity, the observed within-subject difference in VAS score during injection was 33.0 mm with a standard deviation of 24.4 mm. In another study, in subjects with Chinese ethnicity, 43TW1628², comparing Restylane Perlane with and without Lidocaine, the mean within-subject difference in VAS score at injection was 32.0 mm with a standard deviation of 19.5 mm.

However, due to the many injection points in the treatment of the hands, it is believed that the within-subject difference in VAS score will be considerably less in this study than what was seen in the NLFs in the previous two studies referred to. Thus, assuming a true mean within-subject difference of -10 mm and a standard deviation of 25 mm, a significance level of 2.5% and using a one-sided one-sample t-test, inclusion of 68 subjects will give a power of 90% to reject the null hypothesis of > 0 mm within-subject difference. To ensure sufficient power in the event of the need of a non-parametric test for the primary analysis, approximately 15% more subjects will be added

 EST. 1981	Title 43CH2305 Statistical Analysis Plan	Doc id MA-59378
---	--	---------------------------

Study Number 43CH2305
Statistical Analysis Plan

CONFIDENTIAL

Page 16 of 36
Final, 1.0, date 24APR2024

to the 68 needed for the t-test. Hence, approximately 80 subjects will be needed for the primary analysis. In addition, a drop-out rate of 10% is assumed. Thus, approximately 90 subjects will need to be randomized in order to have at least 80 evaluable subjects for the statistical analysis.

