10.4.6 Statistical/Analytical Issues

10.4.6.1 *Adjustments for Covariates*

No adjustment for covariates is planned for the primary, and **CCI** effectiveness analyses.

10.4.6.2 *Handling of Dropouts*

Available data for subjects that drop out will be used up until the time of dropout. Missing values for the primary endpoint will be imputed as described in Section 10.4.6.3.

10.4.6.3 *Handling of Missing Data*

The primary analysis is based on the FAS that includes only subjects that have received treatment in both hands, so the number of missing values for the primary endpoint is expected to be very low. However, any case of missing a primary endpoint value will be imputed by a within-subject difference of 0 mm. This corresponds to assuming no pain relief using Restylane Skinboosters Vital Lidocaine compared to Restylane Vital and is considered as a worst-case approach.

All other endpoints will be analyzed on available data, i.e., no imputations will be done.

10.4.6.4 *Interim Analyses and Data Monitoring*

Not applicable.

10.4.6.5 *Multicenter Study*

The primary endpoint will be presented descriptively for each of the study sites, including CIs. No other by-site subgroup analysis is planned for this study.

10.4.6.6 *Multiple Comparison/Multiplicity*

As there is only one primary endpoint defined for this study, no adjustment for multiplicity is needed for the primary analysis. For the **CCI** no adjustments for multiplicity will be done. P-values obtained for any endpoint other than the primary will be considered descriptive and only provided for ease of interpretation.

10.4.6.7 *Active-Control Studies Intended to Show Equivalence*

Not applicable.

 EST. 1981	Title 43CH2305 Statistical Analysis Plan	Doc id MA-59378
---	--	---------------------------

Study Number 43CH2305
Statistical Analysis Plan

CONFIDENTIAL

Page 30 of 36
Final, 1.0, date 24APR2024

10.4.6.8 *Examination of Subgroups*

No subgroup analyses are planned for this study except for the study site subgroup analysis of the primary endpoint.

10.4.6.9 *Analysis Visits Definition*

Not applicable. All analyses will be performed using nominal visits.

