12.5 Details of the SAS Code for Analysis

The primary and **CCI** endpoints are to be analyzed using one-sample t-tests, or if deemed necessary, Wilcoxon signed-rank tests.

The analysis will be performed at T0, T10, T20, and T30.

The SAS (from the 9.4 version) syntax that will be used to obtain the one-sided p-values of the t-tests is:

```
proc ttest data=<dataset> h0=0 plots(showh0) sides=1 alpha=0.025;
  var <math>\Delta_T</math> variable;
  ods output Ttests=work.Ttests;
run;
```

The SAS (from the 9.4 version) syntax that will be used to obtain the two-sided confidence intervals around the Δ_T estimates is:

```
proc ttest data=<dataset> h0=0 plots(showh0) sides=2 alpha=0.05;
  var <math>\Delta_T</math> variable;
  ods output ConfLimits=work.ConfLimits;
run;
```

	Title 43CH2305 Statistical Analysis Plan	Doc id MA-59378
--	--	---------------------------

Study Number 43CH2305
Statistical Analysis Plan

CONFIDENTIAL

Page 34 of 36
Final, 1.0, date 24APR2024

The SAS (from the 9.4 version) syntax that will be used to obtain the p-values of the Wilcoxon signed-rank tests (in case needed) is:

```
proc univariate data=<dataset> mu0=0;
  var <math>\Delta_T</math> variable >;
  ods output TestsForLocation=
    work.TestsForLocation(where=(Test='Signed Rank'));
run;
```

Note: the univariate procedure only gives two-sided p-values. Thus, the one-sided p-values for the Wilcoxon tests need to be calculated from the obtained two-sided p-values according to the following:

- If the Δ_T estimate is < 0 then the one-sided p-value is calculated as:
 - (two-sided p-value)/2.
- If the Δ_T estimate is ≥ 0 then the one-sided p-value is calculated as:
 - 1-(two-sided p-value)/2.

The SAS (from the 9.4 version) code that will be used to obtain the two-sided confidence intervals around the Δ_T medians (in case Wilcoxon test is used) by using Bootstrapping is:

```
* Define useful macros */
%macro ODSOff(); /* Call prior to BY-group processing */
ods graphics off; ods exclude all; ods noresults;
%mend;

%macro ODSOn(); /* Call after BY-group processing */
ods graphics on; ods exclude none; ods results;
%mend;

proc surveyselect data=<dataset> out=BootSamples noprint seed=59378
  method=urs
  OUTHITS
  samprate=1 reps=10000;

run;

%ODSOff /* suppress output */

proc means data=BootSamples median;
  by Replicate;
  var <math>\Delta_T</math> variable;
  ods output summary=work.summary;
run;

%ODSOn /* enable output */

proc univariate data=summary;

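### The signed-rank test as coded drops the values imputed as 0 mm, so the imputed-FAS and observed-case Wilcoxon tests cannot differ and say nothing about missing data

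*SAP*

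**What the plan says.** The primary analysis is a one-sample t-test on the FAS, judged one-sided: "If the one-sided p-value of the test is <0.025 the pain at the end of injection will be considered statistically significantly lower" (SAP 10.4.2). For missing data, SAP 10.4.6.3 states that "any case of missing a primary endpoint value will be imputed by a within-subject difference of 0 mm". It describes this as assuming no pain relief and as a worst case, and expects very few such values.

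SAP 10.4.3 makes the Wilcoxon signed-rank test a sensitivity analysis if the differences appear non-normal, with the hypotheses restated for the median. It then lists two robustness analyses, observed cases in the FAS and the per-protocol set, and adds: "If the normality assumption is found to be questionable, 1) and 2) will also be performed using the Wilcoxon signed-rank test".

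SAP 12.5 gives the code, "proc univariate data=<dataset> mu0=0", and keeps the signed-rank row of the output. The two-sided p-value is turned into a one-sided one as p/2 if the Δ_T estimate is below 0 and 1 − p/2 otherwise. The SAP does not say whether that estimate is the mean or the median. A separate bootstrap supplies the confidence interval for the median. Neither document says how zero differences are handled in the ranking.

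**The concern.** The imputed value and the tested location are the same number. A signed-rank test at location 0 gives no rank to a difference of 0, so the rule that a missing subject counts as no relief is not carried out in this test. The observed-case repeat is meant to show whether the result depends on the imputation, but here the two results must agree. A reader who saw two matching p-values could take them as evidence that missing data do not matter. The bootstrap median and interval do contain the zeros, so the p-value and interval for the same analysis would rest on different numbers of subjects.

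**Working it through.** **The plan's own figures.** SAP 7 is based on "assuming a true mean within-subject difference of -10 mm and a standard deviation of 25 mm", one-sided 2.5%. With the noncentral t distribution, n = 68 gives power 0.9016 and n = 67 gives 0.8973, so 68 reproduces. The allowance described as "To ensure sufficient power in the event of the need of a non-parametric test for the primary analysis, approximately 15% more subjects" gives 68 × 1.15 = 78.2, or 68/0.85 = 80. Dropout ("a drop-out rate of 10% is assumed") gives 80/0.90 = 88.9, about 90. These values (90 or 80 subjects, −10 mm, SD 25 mm) set the simulations below.

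**Why the two tests coincide.** Let the observed differences be d, and let k missing ones be set to 0. The coded statistic is

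S = (sum of ranks of |d| over d > 0) − n_t(n_t + 1)/4,

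where n_t is the number of differences not equal to 0 and only those are ranked. The k imputed zeros enter neither n_t nor the ranks nor the tie correction. S and the two-sided p-value therefore do not depend on k.

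**One simulated data set** (80 observed whole-mm differences drawn with mean −10 and SD 25; the sample mean was −8.04):

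| Imputed zeros | n_t | S | Coded one-sided p | p with zeros kept in the ranking | t-test p | Mean | Median | Bootstrap 95% CI |
|---|---|---|---|---|---|---|---|---|
| 0 | 77 | −543 | 0.00254 | 0.0035 | 0.00116 | −8.04 | −6 | −11.5 to 1 |
| 8 | 77 | −543 | 0.00254 | 0.0052 | 0.00118 | −7.31 | −2.5 | −9.5 to 0 |
| 10 | 77 | −543 | 0.00254 | 0.0057 | 0.00118 | −7.14 | −1 | −9 to 0 |

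The coded test does not move. The zero-keeping test, the t-test, the median and the interval all do. The mean checks by hand: −8.04 × 80/88 = −7.31.

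**Repeated trials.** In 20,000 simulated trials with 1 to 8 imputed zeros, S and the two-sided p-value never differed between imputed and observed-case data. A separate 24,000 trials (90 subjects; 2, 5 or 9 missing; −10 or −7 mm) also showed no difference.

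**Effect on significance.** At −10 mm with 2 missing, the test is significant in 95.3% of trials as coded and 95.0% with zeros kept, a gap of 0.3 points. With 9 missing the figures are 93.8% and 93.4%, a gap of 0.4 points. Over all settings the gap was about 1 point or less in most runs, and the largest estimate in any set was 1.4.

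**The one-sided conversion.** If the Δ_T estimate is the mean, added zeros cannot change its sign, and the one-sided p-values are identical too. If it is the median, zeros can pull it to 0 and turn p/2 into 1 − p/2. In a second data set (drawn with mean −6; n_t = 78, S = −347.5), 8 imputed zeros moved the median to 0 and the one-sided p from 0.0417 to 0.9583, with S unchanged. In the 20,000 trials at −10 mm this happened 209 times (about 1%) and changed significance 34 times. With 9 of 90 missing it happened in about 3% of trials at −10 mm and 13 to 14% at −7 mm.

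**The case against.** The best defence is that the situation is doubly conditional and secondary. It needs a histogram judged non-normal and a missing T0 value in an FAS limited to subjects treated in both hands. T0 is scored at the end of each hand's treatment, and the left hand is injected only after the right-hand score is complete, so missing values should be few. With none missing, the issue disappears. SAP 10.4.2 and 10.4.3 keep the t-test as the primary analysis and give the Wilcoxon test the job of checking normality. All of that stands and limits the importance of the point.

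Several stronger readings are tempting but not supported:

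- A reader might infer that the plan has no check on missing data. It does: the imputed and observed-case t-tests differ, though weakly, and the per-protocol Wilcoxon can differ because other deviations also exclude subjects.
- A reader might take the 10% in SAP 7 as the share of missing T0 values. It is dropout among randomized subjects. Nine missing is only a stress case.
- A reader might infer that the one-sided p-values always agree. That holds only if the Δ_T estimate is the mean.
- The sample-size text and Protocol 6.4.3.1 might suggest that the Wilcoxon test replaces the t-test as primary. SAP 10.4.3 assigns it a sensitivity role, and this point does not rely on the other reading.
- Ranking missing subjects last against lidocaine would give a much larger effect, but that is a different imputation rule, found nowhere in the plan.

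Neither document says that matching Wilcoxon results will be cited as evidence about missing data, so that risk concerns interpretation and is not a stated intention. What the defence does not answer is that a pair of tests listed under robustness cannot disagree in its statistic or two-sided p-value.

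**Conclusion.** The point holds in a limited form. When normality is doubted and at least one T0 difference is imputed, the coded signed-rank test on the imputed FAS is the observed-case test under another label, and the SAP's imputation rule is not applied in it. The primary t-test is untouched, and the effect on significance is about 1 percentage point or less with 1 to 9 missing (1.4 at most in any set of runs).

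The conclusion assumes that the SAS procedure uses the standard signed-rank definition, which excludes values equal to the tested location; the documents do not state this. The sizes also assume normal whole-mm differences with SD 25 mm and invented numbers of missing values, since the real number is unknown. The undefined Δ_T estimate is a related gap: under the median reading, imputed zeros can reverse the one-sided p-value without any change in the ranks, which is an artefact and not a missing-data check.

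**What to change.** In SAP 10.4.3 and 12.5, preferably before database lock:

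1. Run the imputed-FAS Wilcoxon with ranks that keep zero differences: rank the zeros with the rest and split their rank sum equally between the two signs. An imputed subject then counts as no relief, as SAP 10.4.6.3 intends. Alternatively, leave the code as it is, report a single FAS Wilcoxon labelled observed case, and do not present it as support for the imputed result.
2. Print the number of non-zero differences used beside the FAS n.
3. Define the Δ_T estimate in the one-sided conversion so that imputed zeros cannot change its sign, for example by using the sign of the signed-rank statistic.

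The cost is a few sentences and a few lines of code, with no new data. Keeping the zeros costs about 1 percentage point of significance rate or less in most of the simulated settings. Appending zeros to a test data set and rerunning the SAS code would confirm the behaviour.
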